3.1.4. Modified Intent-to-Treat (mITT) Population

The mITT population includes all subjects in the exposed population who have evaluable immunogenicity results from both Day 1 and at least one later on-study sample.

3.1.5. Immunogenicity Evaluable Population (IEP)

The IEP includes all subjects in the exposed population who:

- Have no important protocol deviation or other reason to be excluded as defined prior to database lock.
- Have not received a prohibited medication.
- Provide evaluable serum sample results for baseline and the primary immunogenicity endpoint within the required time frames:
 - Baseline: Day 1 or within 60 days before study vaccine administration
 - Day 22: Day 19 through Day 25, inclusive

In addition, all subjects in the alphavirus-naïve group are required to be seronegative for both CHIKV and VEEV at baseline, where seronegativity is defined as:

- Anti-CHIKV neutralizing antibody levels below the limit of detection (LOD) of 15, determined by luciferase-based assay (NT80)
- Anti-VEEV neutralizing antibody levels below the LOD of 20, determined by Plaque-Reduction Neutralization Test (PRNT80) assay,

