1.1.2 Venezuelan Equine Encephalitis Virus and Vaccines

Venezuelan equine encephalitis virus (VEEV) is an alphavirus related to CHIKV (Figure 2). Humans infected with VEEV develop a febrile illness, often with severe headache, averaging 1–5 days after exposure. Dissipation of febrile illness coincides with the production of neutralizing antibodies. The average case fatality rate of VEEV is <1%. Children have more severe disease, are more likely to develop encephalitis and can be left with severe neurological complications.

VEEV has been recognized as a potential biological weapon because of its high attack rate with a debilitating illness and its adaptability to aerosol dissemination. Accordingly, the US Army has invested much research in this pathogen and developed experimental vaccines to protect those who handle VEEV in the laboratory ([Wolfe 2013](#)).

Figure 2: Phylogenetic tree of alphaviruses showing the relative positions of CHIKV and the IAB strain of VEEV from which the TC83 vaccine was made.

Two vaccines for VEEV administered to laboratory workers at USAMRIID under IND are a live attenuated virus vaccine (TC83) and an inactivated virus vaccine (TC84). TC-83 was created by serially passaging the Trinidad Donkey VEEV strain in guinea pig heart cells and point mutations in E2 and the 5' untranslated region are responsible for the attenuated phenotype of TC-83 ([Taylor 2017](#)). TC83 is the most widely used but has a significant (26%) non-response rate. Non-responders who require immunity are generally offered the inactivated TC84 vaccine.

Laboratory workers at USAMRIID may have also received investigational formalin-inactivated vaccines for Eastern Equine Encephalitis (EEEV) and/or Western Equine Encephalitis (WEEV) Viruses ([Reisler 2012](#)).

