The NIH's VRC 704 was a Phase 2 trial conducted at multiple CHIK-endemic sites in the Caribbean ([Chen 2018](#)). The study was a double-blind, placebo-controlled study with 200 subjects receiving 20 μ g of CHIKV-VLP and 200 receiving placebo in a 2-dose series at Weeks 0 and 4. The study was initiated in 2016 and completed in 2018. Approximately 20% of subjects demonstrated detectable anti-CHIKV neutralizing antibodies at baseline. CHIKV-VLP appeared safe and well tolerated in subjects who were followed through Week 72, with no related SAEs or other safety concerns. CHIKV-VLP appeared highly immunogenic, with a GMT of 2004.5 and 99.5% of recipients having neutralizing antibodies at Week 8. A boosting effect of CHIKV-VLP was also observed in subjects with baseline anti-CHIKV neutralizing antibodies.

Specimens from VRC 704 were also analyzed at Emergent, using the CHIKV 181/25 luciferase assay. A sub-analysis was performed on subjects without pre-existing anti-CHIKV neutralizing activity. Using a more stringent 80% neutralization cutoff (NT₈₀), the GMT was 123 at Week 4 and 1701 at Week 8. Although antibody levels declined with time, as would be expected, the GMT

remained ≥ 100 for at least 18 months, indicating that long-term protection can potentially be achieved without the need for booster doses. These results demonstrated that CHIKV-VLP was safe and immunogenic in adults in CHIKV-endemic areas, including those with serologic evidence of previous CHIKV exposure. The most frequently reported local adverse event was pain/tenderness at the injection site reported as mild by 58 of 197 (29%) vaccine recipients who received at least one study injection and as moderate by 3/197 vaccine recipients (2.0%). The most frequently reported systemic adverse events were mild or moderate headache reported by 53 of 197 (27%) vaccine recipients, malaise (53/197, 25.6%), and myalgia (46/197, 23.4%). Placebo recipients reported these systemic reactogenicity symptoms at similar frequencies. One vaccine recipient (0.5%) experienced a headache graded as severe following the second vaccination. A total of 16 SAEs in 15 (3.8%) subjects were reported, all were assessed as unrelated to the study vaccine. All potentially related AEs resolved without clinical sequelae.

Taken together, the findings from VRC 311 and VRC 704 suggest that a single dose of 40 mcg CHIKVLP059VP is well-tolerated and immunogenic in both CHIKV-exposed and CHIKV-naïve adults.

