2.8.2 Exclusion Criteria

Subjects who meet any of the following criteria cannot be enrolled:

1. Acute disease or febrile illness at the time of enrollment.
2. Clinically significant cardiac, respiratory, rheumatologic or other medical or psychiatric condition that, in the opinion of the Investigator, places the subject at increased risk or affects their ability to understand and comply with study procedures.

3. Abnormal screening lab test results that, in the opinion of the investigator, obscures interpretation of the safety data or suggests a clinically significant cardiac, respiratory, rheumatologic or other medical condition that places the subject at increased risk.
4. Pregnant, lactating or planning to become pregnant during the study period.
5. Laboratory evidence of infection with Hepatitis B, C or HIV.
6. History of naturally (non-laboratory) acquired chikungunya or other alphavirus infection or travel to a WHO-designated chikungunya-endemic region within 30 days prior to Day 1.
7. History of acute allergic reaction to any component of CHIKV-VLP vaccine, or Alhydrogel®.
8. Current (30 days prior to Day 1) or anticipated use of systemic immunomodulatory or immunosuppressive medications.
9. History of splenectomy, immunosuppressive condition, autoimmune disease, or immunodeficient condition.
10. Family history of congenital or hereditary immunodeficiency.
11. Suspected or known current alcohol abuse that, in the opinion of the investigator, would interfere with their ability to understand and comply with study procedures.
12. Current intravenous drug use.
13. Prior receipt of an investigational chikungunya vaccine.
14. Receipt or planned receipt of any licensed vaccine from 30 days prior to Day 1 through the Day 29 study visit.
15. Participation in another clinical trial during the study period in which an investigational product is administered.
16. For the alphavirus naïve group, history of prior alphavirus vaccination is exclusionary.

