4.7.1 Safety labs

At screening, blood will be collected for serum testing for HBV, HCV and HIV and seropositive subjects excluded. Overall health will be assessed with a complete blood count, creatinine, and liver associated enzymes (AST/ALT) at screening and Days 1 and 8.

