6.2.1. Analysis Methods for Secondary Immunogenicity Endpoints

The same method used for the primary immunogenicity analysis, excluding the estimated difference, will also be used for the secondary analysis of seroresponse rate, comparing the proportion of prior alpha subjects to the proportion of naïve alpha subjects having seroresponse by anti-CHIKV neutralizing antibodies on Days 8, 29, 57 and 182 and by anti-CHIKV total antibodies and anti-VEEV total and neutralizing antibodies on Days 22 and 29.

For the secondary analysis of GMT and GMR, the GMTs and GMRs at the specified time points will be compared for differences between the two study arms (prior alpha vs. naïve alpha) for each type of antibody listed above.

The primary model used for the immunogenicity evaluable population is an analysis of variance (ANOVA), with logarithmically-transformed (\log_{10}) titers as the dependent variable and study arm, age, and gender as the predictor variables in the model. The primary model used for the mITT population is the same except that \log_{10} baseline titer will be added as a predictor if there are subjects with measurable titers in the naïve alpha group at baseline. If any baseline titer is equal to zero, then one will be added to all baseline titers prior to taking the log. The least square means estimated from the ANOVA (or ANCOVA) and their 95% CIs will be back-transformed and reported as the group GMT values. The geometric mean ratio of the prior alpha group to the naïve alpha group, and its 95% CI, will be calculated by specifying a linear contrast between the groups in the model. Since the linear contrast yields a difference between groups in log-transformed space, the difference will be exponentiated to produce a geometric mean ratio of one group to the other. The p-value associated with each model comparison will also be reported. Additionally, the median, minimum and maximum will be summarized based on the non-transformed scale.

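### The IEP screens out baseline CHIKV seropositivity in the naïve arm only, and neither GMT model adjusts for it when it occurs only in the prior arm

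*SAP*

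**What the plan says.** **Analysis population.** SAP 3.1.5 adds a serostatus condition to the IEP: "all subjects in the alphavirus-naïve group are required to be seronegative for both CHIKV and VEEV at baseline". For CHIKV, seronegative means a luciferase NT80 below the limit of detection of 15. SAP section 8 explains that the condition answers an FDA comment. No CHIKV condition is set for the prior arm. The mITT population (SAP 3.1.4) has no serostatus condition for either arm.

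**Eligibility.** Protocol 2.8.2, repeated in SAP 1.4, applies exclusion 6 to both arms: "History of naturally (non-laboratory) acquired chikungunya or other alphavirus infection". Exclusion 13 bars "Prior receipt of an investigational chikungunya vaccine". Protocol 4.7.1 describes the screening serology: "At screening, blood will be collected for serum testing for HBV, HCV and HIV and seropositive subjects excluded". CHIKV serology is not part of it.

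**Models.** Protocol 9.6 specifies an ANCOVA for GMT with log-transformed baseline titer as covariate. SAP 6.2.1 replaces this in the IEP by a model with arm, age and gender. In the mITT, log10 baseline titer is added "if there are subjects with measurable titers in the naïve alpha group at baseline". SAP section 8 does not list this change among its departures from the protocol. It does record that the logistic sensitivity models were dropped; in Protocol 9.6 those models included baseline titer.

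**The concern.** The trial asks what earlier exposure to a *heterologous* alphavirus vaccine does to the response to this vaccine. Immunity to CHIKV itself is a different factor, and the protocol's account of the VRC 704 study shows that it matters: "A boosting effect of CHIKV-VLP was also observed in subjects with baseline anti-CHIKV neutralizing antibodies".

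The prior arm is recruited from USAMRIID, where Protocol 1.1.2 places these vaccines among laboratory staff: "Laboratory workers at USAMRIID may have also received investigational formalin-inactivated vaccines". A past laboratory CHIKV infection, or one that nobody recognised, would pass eligibility in either arm. The IEP would then remove that subject from the naïve arm and keep a similar subject in the prior arm.

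A retained subject of this kind starts with antibody and is boosted. That raises the prior arm's anti-CHIKV GMT, the GMR and the proportions above titers of 40, 100, 160 and 640. The effect is to hide interference or to look like enhancement. The IEP model has no term to absorb it, and the mITT model takes no account of measurable titers that occur only in the prior arm.

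**Working it through.** **1. The plan's own figure.** The plan gives no figure for this issue. The nearest is 80% power for 65% versus 95% seroconversion with 30 per arm (Protocol 9.1). Exact enumeration of the two-sided Fisher test gives 78.8%, so that figure is not in dispute.

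**2. Path of a CHIKV-immune subject, by arm**

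| Step | Naïve arm | Prior arm |
|---|---|---|
| Exclusion 6, laboratory-acquired CHIKV | admitted | admitted |
| Screening serology | not tested for CHIKV | not tested for CHIKV |
| IEP, baseline NT80 of 15 or more | removed | kept |
| IEP model, baseline titer | none | none |
| mITT, subject kept | yes | yes |
| mITT, measurable titer triggers covariate | yes | no |

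The asymmetry comes from the IEP rule and the covariate trigger. It does not come from eligibility.

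**3. Effect on the prior-arm GMT.** Let k of n = 30 prior-arm subjects have Day 22 titers r-fold higher than they would otherwise have. The arm's geometric mean is multiplied by r^(k/30). The planned n is 30; k and r are assumptions.

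| r | k = 1 | k = 2 | k = 3 |
|---|---|---|---|
| 4 | 1.05 | 1.10 | 1.15 |
| 8 | 1.07 | 1.15 | 1.23 |
| 10 | 1.08 | 1.17 | 1.26 |

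For example, 10^(3/30) = 10^0.1 = 1.26. The GMR against the naïve arm moves by the same factor, apart from the adjustment for age and gender.

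**4. Effect on thresholds.** Each such subject who would otherwise have missed a threshold adds 1/30 = 3.3 points. Suppose every subject has a 4-fold rise at Day 22, as Addendum 1 indicates. Then a baseline of 160 guarantees at least 4 × 160 = 640 at Day 22, and a baseline of 40 guarantees at least 160.

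**5. Does the fold-rise analysis remove it?** SAP 6.2.1 also compares geometric mean fold-increase. SAP 3.3 sets values below the limit to 15 for fold-increase. Suppose a subject with a baseline below 15 would reach titer T, for a fold-rise of T/15. A pre-immune subject with baseline B reaching rT has a fold-rise of rT/B. The arm's geometric mean fold-rise is then multiplied by (15r/B)^(k/30). With r = 10, B = 320 and k = 3 (assumed), this is (150/320)^0.1 = 0.93. The GMT would rise by 26% while the fold-rise fell by 7%. With r = 10 and B below 150, both would rise. A divergence can therefore signal the problem, but neither analysis is free of it.

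**6. Scale against precision.** Assume a log10 SD of 0.3 to 0.5 and 30 per arm. The 95% limits of the GMR lie a factor of 10^(2.00 × SD × √(2/30)) from the estimate, which is about 1.4 to 1.8. Every shift in step 3 is smaller than that.

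**The case against.** **The primary endpoint.** A reader might infer that the one-sided rule biases the primary result towards false interference. A subject below the limit needs only 4 × 15 = 60 for seroresponse, whereas a prior-arm subject with baseline 320 needs 1280. The documents do not support this as a realised harm. Addendum 1 reports, for both IEP and mITT, that all subjects had a 4-fold rise by the second time point. It adds that the cumulative tables would have matched the by-visit ones. The second time point is Day 22 at the latest, if counting starts at Day 8. No prior-arm subject then failed through a high baseline, and restricting the comparison would leave 100% against 100%.

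**Eligibility.** A reader might also infer that laboratory-acquired infection is allowed in the prior arm alone. Exclusion 6 is worded identically for both arms. The documents report no laboratory CHIKV infection and do not say that these workers handled CHIKV.

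**Existing safeguards.** It would be too strong to say that the plan takes no account of baseline. Fold-rise is compared between arms. Day 1 GMTs and threshold proportions are summarised by arm, and all titers are listed (Listing 16.2.6.1). The anti-CHIKV neutralizing analyses are repeated in the mITT. These would show a marked imbalance, such as a baseline of 320. They do not remove it, and no table counts subjects at the cut-off of 15.

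**Rationale for asymmetry.** Confirming that controls are truly naïve is sensible. In the prior arm, low CHIKV reactivity may be cross-neutralization from the vaccines under study, so removing it could remove part of the effect. This objection stands, and it is why the remedy should not replace the IEP.

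**Conclusion.** The point holds, but it is limited to the anti-CHIKV GMT/GMR and titer-threshold comparisons. In the IEP, homologous CHIKV immunity is filtered out of one arm and neither filtered nor modelled in the other. In the mITT, it is modelled only if naïve subjects also have measurable titers.

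The size depends on two quantities that the documents do not give: how many prior-arm subjects were CHIKV-seropositive at baseline, and how much higher their titers were. The number may be zero, in which case nothing changes. With 1 to 3 of 30 and a 10-fold excess, the prior-arm GMT is inflated by 8%, 17% or 26%. With a 4-fold excess the range is 5% to 15%. These are modest shifts beside the likely width of the interval, but their direction favours finding no interference. With seroresponse at 100% in both arms, these secondary comparisons carry most of the remaining information on interference. The primary seroresponse result is not expected to change.

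**What to change.** 1. **SAP 6.2.1, mITT model:** let log10 baseline titer enter when *either* arm has measurable baseline titers. If only the prior arm has them, the slope is estimated from that arm alone, so this should be read together with item 2.
2. **Sensitivity analysis:** repeat the anti-CHIKV neutralizing GMT/GMR and threshold analyses in IEP subjects with baseline CHIKV NT80 below 15 in both arms. The VEEV condition stays naïve-only, because VEEV antibody in the prior arm reflects the exposure being studied.
3. **Reporting:** give the number of baseline CHIKV-seropositive subjects (NT80 of 15 or more) in each arm. If it is zero in the prior arm, one sentence closes the matter.

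The cost is SAP wording and a rerun on a subset. Protocol 4.7.2 already schedules Day 1 NT80. Because Addendum 1 describes decisions after database lock, the added analysis should be labelled post hoc. The main drawback is that prior-arm subjects whose CHIKV reactivity is cross-reaction from the studied vaccines are also set aside. For that reason it should remain a sensitivity analysis beside the IEP.

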3.2. Missing Data and Outliers

Missing Data

A missing datum for a given study visit may be due to the fact that:

1. data were not collected for the visit or were unusable, or
2. a subject permanently discontinued from the study before reaching the assessment.

There are no plans to impute values for missing data points except for imputing missing relationship to study drug for AEs as related.

3.3. Data Handling Conventions and Transformations

By-subject listings will be presented for all enrolled subjects sorted by subject ID number, study arm, visit date, and time (if applicable). Data collected on log forms, such as AEs, will be presented in chronological order within subject.

Baseline is defined as the Day 1 value. If the Day 1 value is missing, then the last non-missing value prior to Day 1 will be used as the baseline value.

Data that are less than the limit of detection (LOD) or above the upper limit of assay reporting will be imputed as follows:

- Antibody titer assay results that are reported as less than the LOD will be imputed as the LOD/2 when calculating geometric mean titer (GMT) and geometric mean ratio (GMR). For example, if the LOD is 15 and a result is noted as “<15”, a titer of 15/2 (=7.5) will be imputed.
- For fold increase over baseline in antibody titer, if a value is < LOD, it will be imputed as the LOD. For example, if the LOD is 15 and a result is noted as “<15”, a titer of 15 will be imputed.
- A value that is one unit above the upper limit of assay reporting will be used for calculation of descriptive statistics if the datum is reported in the form of “> x” (where x is considered the limit of quantitation). Values with decimal points will follow the same logic as above.

3.4. Visit Windows

For determination of Baseline visit and all other visits, an analysis visit will be derived to summarize the data by the proper visit window interval.

The following algorithm will be used for the study day determination:

- Day 1 = Day of Vaccination;
- If Date of Assessment/Visit \geq Date of Vaccination then Study Day = (Date of Assessment/Visit - Date of Vaccination) + 1;
- If Date of Assessment/Visit < Date of Vaccination then Study Day = (Date of Assessment/Visit - Date of Vaccination).

4. SUBJECT DISPOSITION

4.1. Study Arms

All subjects who do not fail screening will fall into one of two study arms based on their prior exposure to an investigational heterologous alphavirus vaccine. The group of subjects who had prior exposure will be referred to as the "prior alpha" study arm and the group of subjects who had no prior exposure will be referred to as the "naïve alpha" study arm throughout the remainder of this document. Regardless of pre-exposure status, subjects will receive one injection of the study drug (PXVX0317) on Day 1.

4.2. Summary of Subjects by Site

The number and percent of subjects will be summarized by site for each study arm (prior alpha vs. naïve alpha) and overall. The percentage calculations will be based on the number of subjects in the exposed population.

4.3. Disposition of Subjects

A summary of subject disposition will be provided by study arm and overall. This summary will present the number of subjects who completed through Day 182 and discontinued from the study early along with the primary reason for discontinuing the study early. No p-values or inferences based upon comparison of disposition in the study arms will be generated.

A data listing of reasons for early study discontinuation will be provided as well as a listing of reasons for screen failure.

5. BASELINE DATA

5.1. Demographics

Subject demographic and baseline data (e.g., age, age group (18-31, 32-45, 46-55, and 56-65 years), sex, ethnicity, race, weight, height, body mass index (BMI), time since prior alphavirus vaccine, and prior alphavirus vaccine titer) will be summarized by study arm and overall using descriptive statistics for continuous data and by the number and percent of subjects for categorical data. Age and time since prior alphavirus vaccine will be calculated in years at the time of vaccination. No p-values or inferences regarding comparisons of baseline demographics between the two study arms will be provided.

The summary will be provided for the safety, immunogenicity evaluable, and mITT populations. A listing of demographic data will be provided for the enrolled population.

5.2. Medical History

Medical history will be coded using version 20.1 of the Medical Dictionary for Regulatory Activities (MedDRA). Medical history will be summarized by system organ class (SOC), preferred term (PT), study arm, and overall for the safety population. Medical history will also be listed for the exposed population.

6. PRIMARY, SECONDARY, AND EXPLORATORY ANALYSES

The treatment period begins and ends at the time of vaccination at baseline (Day 1). The observation period spans Day 1 post-vaccination through Day 29, and follow-up period spans the time following the Day 29 visit through Day 182.

The primary and secondary analyses will be performed once all data have been collected from all subjects through their Day 182 follow-up visit and all EDC and laboratory data records have been cleaned and signed off by the PI.

